9.3.3 Removal of Subjects From Therapy or Assessment

The investigator may withdraw the subject from the study at any time for safety or administrative reasons. The subject may stop study drug or withdraw from the study at any time for any reason.

The reason for discontinuation will be documented. If a subject discontinues study treatment, the subject will enter the Follow-Up Period and complete protocol-specified off-treatment visits and procedures. The investigator should confirm whether a subject will withdraw from study treatment but agree to continue protocol-specified, off-treatment study visits, procedures, or whether the subject will withdraw from the study. If a subject or guardian/legally authorized representative withdraws consent (or assent), the date will be documented in the source documents.

A subject who discontinues study treatment should be followed for subsequent protocol-specified visits and procedures. If a subject discontinues study drug but remains in the study, the set of end-of-treatment procedures, Early Treatment Discontinuation according to Early Discontinuation Visit schedule, will be administered, and further information will be collected at visits according to regular Schedule of Procedures/Assessments. The primary reason for discontinuation and all other reasons contributing to the subject’s discontinuation from study drug will be collected. If a subject discontinues from study treatment and the study at the same time, Early Discontinuation Visit will be conducted followed by safety Follow-up Visit (see [Section 9.5.5](#)).

9.4 Treatments

9.4.1 Treatments Administered

The following study drugs will be used in this study:

- Test drug: E2023, oral, 10-mg tablets
- Comparator drug: placebo, oral tablets matching the test drug

Selection of dose, timing, and instruction on how to prepare suspension for individual subjects is described in [Section 9.4.5](#).

9.4.2 Identity of Investigational Products

Lorcaserin and matching placebo will be provided as a blue-colored, film-coated, 10-mg tablet, round, biconvex, debossed “A” on one side and “10” on the other side.

Investigational products, ie, lorcaserin and placebo, will be supplied by the sponsor in blinded labeled containers.

The sponsor will provide the study drugs packaged in a double-blind configuration. Each subject’s study drug will consist of either lorcaserin or placebo.

9.4.2.1 Chemical Name of E2023

- Test drug code: E2023
- Generic name: Lorcaserin
- Chemical name: (R)-8-chloro-1-methyl-2,3,4,5-tetrahydro-1H-3-benzazepine hydrochloride hemihydrate
- Molecular formula: $C_{11}H_{14}ClN \cdot HCl \cdot 0.5 H_2O$
- Molecular weight: 241.16 g/mol

9.4.2.2 Comparator Drug

The comparator drug is placebo, oral tablets matching the test drug.

9.4.2.3 Labeling for Study Drug

Lorcaserin or matching placebo will be labeled in accordance with text that is in full regulatory compliance with each participating country and is translated into the required language(s) for each of those countries.

9.4.2.4 Storage Conditions

Study drug will be stored in accordance with the labeled storage conditions. Temperature monitoring is required at the storage location to ensure that the study drug is maintained within an established temperature range. The investigator or designee is responsible for ensuring that the temperature is monitored throughout the total duration of the study and that records are maintained; the temperature should be monitored continuously by using either an in-house validated data acquisition system, a mechanical recording device, such as a calibrated chart recorder, or by manual means, such that minimum and maximum thermometric values over a specific time period can be recorded and retrieved as required.

9.4.3 Method of Assigning Subjects to Treatment Groups

Subjects will be assigned to treatments based on a computer-generated randomization scheme that will be reviewed and approved by an independent statistician. The randomization scheme and identification for each subject will be included in the final clinical study report for this study.

After the Baseline Period, subjects will be randomized to 1 of 2 treatment groups in a ratio of 1:1. Each treatment group will receive either lorcaserin or placebo BID.

Randomization will be performed centrally by an interactive voice and web response system (IxRS). The IxRS or clinical supply vendor will generate the randomized bottle identification numbers. At enrollment (and after successful completion of Visit 1), the investigator or designee will call the IxRS to register the subject information. At randomization (Visit 2), the IxRS will assign each subject a unique 6-digit randomization number. At every subsequent dose change, the investigator or a designee will call the IxRS to obtain dispensing instructions and register the subject's visit.

9.4.4 Selection of Doses in the Study

Population pharmacokinetic (POPK) modeling of lorcaserin in a pooled population of healthy adult volunteers from 2 Phase 1 studies, and overweight and obese adults from 1 Phase 2 study and 3 Phase 3 studies (Report CMPS-APD356-003R), has identified that the PK profile of lorcaserin is best described by a 1-compartment model with first order absorption and elimination. The analysis also identified that exposures to lorcaserin are a function of body weight, with allometric body weight effects on both clearance (exponent=0.75) and volume of distribution (exponent=1).

In addition, a physiologically-based pharmacokinetic (PBPK) model was developed for lorcaserin using Simcyp V19. Performance of the model in predicting lorcaserin PK was verified by plotting the model-predicted PK profiles over the observed lorcaserin PK profiles in healthy volunteers from Studies APD356-001 (single ascending dose), APD356-002 (multiple ascending dose) and APD356-101 (immediate-release vs extended-release bioequivalence study). Overall, the model predicted the PK profiles of lorcaserin well and was considered suitable for predicting lorcaserin PK profiles in children.

Both the POPPK model and the PBPK model were used to simulate lorcaserin PK profiles for a range of doses and body weights in children ([Centers for Disease Control and Prevention, 2020](#)). The lower limit of the body weight for Group 1 (10 kg), represents the 10th percentile of body weight distribution in a 2 year-old child, according to the Centers for Disease Control and Prevention. PBPK simulations of lorcaserin PK profiles were performed using the default values of the Simcyp Pediatric population file. Both methods predicted similar PK profiles for lorcaserin in the age range evaluated (2 to 7 years).

The doses of lorcaserin proposed for this study were selected based on the similarities of the predicted PK profile with those predicted after lorcaserin 10 mg BID administration in a 70 kg adult.

The doses proposed are further supported by data from a Good Laboratory Practice repeated-dose toxicity study in juvenile Sprague Dawley rats at doses of 0, 5, 50, and 100 mg/kg/day. Juvenile and adult Sprague Dawley rats tolerate lorcaserin at similar doses and exposures and the toxicity profile of lorcaserin is similar between juvenile and adult rats. Significant findings noted in the juvenile toxicity study were delayed sexual maturity in females and increased incidence and extent of tubuloalveolar glandular tissue of mammary gland in males compatible with increased prolactin levels at the highest dose tested (100 mg/kg/day). These findings were absent at the mid-dose (50 mg/kg/day) providing 15- and 10-fold exposure margins in females and males, respectively, relative to the highest anticipated mean daily exposure in the proposed clinical study (10 mg BID for a 40 kg child).

9.4.5 Selection and Timing of Dose for Each Subject

During the Treatment Period, all subjects will take study drug as a suspension BID approximately 12 hours apart based on weight according to [Table 1](#).

Table 1 Selection of Dose

Subject's Weight	10 to <20 kg	20 to <40 kg	≥40 kg
Target Dose(starting)	2.5 mg BID (5 mg/day)	5 mg BID (10 mg/day)	10 mg BID (20 mg/day)
Dose Level Step (optional)	2.5 mg BID (5 mg/day)	5 mg BID (10 mg/day)	—
Maximum Dose	5 mg BID (10 mg/day)	10 mg BID (20 mg/day)	10 mg BID (20 mg/day)

BID = twice daily.

To prepare the suspension of study drug before each administration, 2 tablets (from a blister pack, assigned by IxRS) will first be suspended in 10 mL of water, after which 70 mL of sugar-free Ora-Sweet Syrup will be added and the suspension mixed thoroughly. For subjects with weight <20 kg, a 20 mL aliquot of this suspension, or for subjects with weight ≥20 kg, a 40 mL aliquot of this suspension will be taken orally and the remainder of the suspension should be discarded after each administration (for details see [Appendix 3](#)).

9.4.6 Blinding

During the Randomization Phase, subjects and all personnel involved with the conduct and interpretation of the study, including investigators, site personnel, and sponsor staff will be blinded to the treatment codes. Randomization data will be kept strictly confidential, filed securely by an appropriate group with the sponsor or CRO and accessible only to authorized persons (eg, Eisai Global Safety) until the time of unblinding, per SOP.

9.4.7 Prior and Concomitant Therapy

Any medication (including over-the-counter medications) or therapy administered to the subject during the study starting at the date of informed consent (or assent) will be recorded. The AE or medical condition for which the concomitant medication or therapy was administered will be recorded.

Concomitant AEDs, including Epidiolex®, initiated before Screening are allowed; the dose must remain stable during the Prerandomization and Randomization Phase.

Benzodiazepines are allowed as AEDs or rescue medication for seizure control.

The following medications are prohibited during the Prerandomization and Randomization Phase: Artisanal cannabidiol products, serotonergic drugs (due to the risk of serotonin syndrome), including selective serotonin reuptake inhibitors, serotonin-norepinephrine reuptake inhibitors, monoamine oxidase inhibitors, triptans, bupropion, dextromethorphan, centrally-acting anorectic agents including fenfluramine, and St. John's Wort.

Drugs that are cytochrome P450 2D6 substrates should be used with caution, as lorcaserin can increase exposure of these drugs.

Investigational drugs or devices are prohibited during the participation in the study.

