The following medications are prohibited during the Prerandomization and Randomization Phase: artisanal cannabidiol products, serotonergic drugs (due to the risk of serotonin syndrome), including selective serotonin reuptake inhibitors, serotonin-norepinephrine reuptake inhibitors, monoamine oxidase inhibitors, triptans, bupropion, dextromethorphan, centrally-acting anorectic agents including fenfluramine, and St. John's Wort.

Drugs that are cytochrome P450 2D6 substrates should be used with caution, as lorcaserin can increase exposure of these drugs.

Investigational drugs or devices are prohibited during the participation in the study.

Assessments

Efficacy Assessments

Seizure diaries will be used to collect seizure counts.

CGIC (clinician-rated) will be assessed. CGIC is a 7-point scale that provides a clinician-determined summary measure of change from baseline of subject's clinical status.

Pharmacokinetic Assessments

Blood samples for PK assessment will be collected during the Treatment Period.

Pharmacodynamic, Pharmacogenomic, and Other Biomarker Assessments

Data may be analyzed based on types of genetic mutations related to epilepsy (information on genetic mutation related to epilepsy will be collected, if available, based on review of epilepsy history).

Safety Assessments

Safety assessments will consist of monitoring and recording all AEs; regular laboratory evaluation for hematology, blood chemistry, and urinalysis; periodic measurement of vital signs, weight, echocardiograms, and ECGs; and the performance of physical and neurological examinations. An assessment of suicidality using the C-SSRS (for subjects aged ≥ 6 years old) or based upon clinical assessment of the investigator (for subjects < 6 years old) will be performed at every study visit.

The C-SSRS provides assessment of suicide risk including the severity and immediacy of that risk through a series of plain-language questions.

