9 INVESTIGATIONAL PLAN

9.1 Overall Study Design and Plan

This is a multicenter, multiple-dose, randomized, double-blind, placebo-controlled, parallel-group adjunctive therapy study in subjects with Dravet syndrome. The study will consist of a Core Study and open-label Extension Phase.

The Core Study will include a Prerandomization and a Randomization Phase.

The Prerandomization Phase will include a Screening/Baseline Period (4 weeks), during which the subjects will be assessed for eligibility.

Once the Screening and Baseline procedures have been completed and eligibility has been established, the subjects will be randomized and begin treatment in the Randomization Phase. Approximately 58 subjects will be randomized to 1 of 2 treatment groups in a ratio of 1:1 and will receive lorcaserin or placebo for 14 weeks. The randomization will be stratified by previous treatment with fenfluramine (yes/no) and by weight categories (10 to <20 kg, 20 to <40 kg, and \geq 40 kg).

The Randomization Phase will consist of 2 periods: Treatment Period (14 weeks) and Follow-up Period (4 weeks).

During the Treatment Period, all subjects will take study drug twice daily (BID) based on weight as described in [Section 9.4.1](#).

For lower weight categories, during the first 2 weeks of Treatment Period, depending on the subject's clinical response and tolerability, the dose may be increased (not earlier than after 1 week of treatment) by 1 dose level at a visit. If the dose was increased, in the event of AEs, according to the investigator's clinical judgment, the dose may remain the same or can be decreased by 1 dose level, to the Target dose at any time during the Treatment Period. If the dose had been decreased, it may be increased again if tolerability improves.

All subjects who complete the Core Study will be eligible to enter the Extension Phase (refer to [Appendix 2](#)). The last visit of the Treatment Period of the Core Study is considered to be the 1st visit of the Extension Phase.

The Follow-up Visit will be conducted 4 weeks after the last dose of study drug for subjects who do not enter the Extension Phase.

An overview of the study design is presented in [Figure 1](#).

[figure not shown]

Figure 1 Study Design: E2023-A001-304 Core Study and Extension Phase

Follow-up can occur during the Randomization Phase (if the subject discontinued during the Randomization Phase), or during the Extension Phase, after the termination of study treatment.

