9.1.3 Extension Phase

The Extension Phase will consist of a Treatment Period (12 weeks) and a Follow-up Period (4 weeks). Subjects are eligible to complete the Extension Phase only if they have completed the Treatment Period of the Core Study.

All subjects will receive lorcaserin during the entire Extension Phase but the dose level will be blinded during the first 6 weeks. During the first 6 weeks of the Extension Phase, subjects who received lorcaserin during the Core Study will receive the same dose of lorcaserin (the dose will remain flexible per weight category, based on clinical response and tolerability); subjects who received placebo during the Core Study will receive the target dose of lorcaserin per weight category. During the second 6 weeks of the Extension Phase, all subjects will receive lorcaserin at the maximum dose per weight category (the dose may be decreased due to tolerability reasons and increased again if tolerability improves). Addition, deletion, and dose changes to concomitant AEDs are not allowed during the Treatment Period of the Extension Phase.

The Follow-up Visit will be conducted 4 weeks after the last dose of study drug for subjects who will not participate in the Extended Access Program (Study E2023-A001-405) after completion of this study. Subjects who complete the Extension Phase will be eligible to enter into Study E2023-A001-405. See [Appendix 2](#) for a full description of the Extension Phase.

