9.3.2 Exclusion Criteria

Subjects who meet any of the following criteria will be excluded from this study:

1. Females who are breastfeeding or pregnant at Screening or Baseline (as documented by a positive beta-human chorionic gonadotropin). A separate baseline assessment is required if a negative screening pregnancy test was obtained more than 72 hours before the first dose of study drug.
2. Females of childbearing potential who:
 - Within 28 days before study entry, did not use a highly effective method of contraception, which includes any of the following:
 - Total abstinence (if it is their preferred and usual lifestyle)
 - An intrauterine device or intrauterine hormone-releasing system
 - A contraceptive implant
 - An oral contraceptive (Subject must have been on a stable dose of the same oral contraceptive product for at least 28 days before dosing and must agree to stay on the same dose of the oral contraceptive throughout the study and for 28 days after study drug discontinuation).
 - Have a vasectomized partner with confirmed azoospermia
 - Do not agree to use a highly effective method of contraception (as described above) throughout the entire study period and for 28 days after study drug discontinuation.

NOTE: All postmenarche females will be considered to be of childbearing potential unless they are postmenopausal (amenorrheic for at least 12 consecutive months, in the appropriate age group, and without other known or suspected cause) or have been sterilized surgically (ie, bilateral tubal ligation, total hysterectomy, or bilateral oophorectomy, all with surgery at least 1 month before dosing).

3. Use of lorcaserin within 4 weeks before Screening, or any history of it being discontinued due to lack of efficacy or adverse reactions
4. Use of fenfluramine within 2 months before Screening, any history of lack of fenfluramine efficacy, or any history of valvulopathy at baseline with history of fenfluramine use
5. Use of serotonergic or other prohibited drugs administered within 7 days (or 5 half-lives, whichever is longer) or monoamine oxidase inhibitors within 30 days before dosing
6. Has a history of status epilepticus that required hospitalization during the 6 months before Screening
7. Currently has progressive CNS disease, other than Dravet syndrome, including degenerative CNS diseases and progressive tumors
8. Any history of malignancies

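### The ban on serotonergic drugs stops at the end of the Core Study, although every subject takes lorcaserin in the 12-week Extension Phase

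*Protocol*

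**What the plan says.** Protocol Section 9.4.7 introduces the banned list with "The following medications are prohibited during the Prerandomization and Randomization Phase". The list names artisanal cannabidiol, SSRIs, SNRIs, MAO inhibitors, triptans, bupropion, dextromethorphan, centrally acting anorectics including fenfluramine, and St. John's Wort. The synopsis carries the same list with the same limit, and both places give the reason for the serotonergic group: "serotonergic drugs (due to the risk of serotonin syndrome".

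Section 9.1 defines the phases: "The study will consist of a Core Study and open-label Extension Phase", and "The Core Study will include a Prerandomization and a Randomization Phase". Section 9.1.3 and Appendix 2 then describe a 12-week Extension in which everyone receives lorcaserin. In its first 6 weeks, "subjects who received placebo during the Core Study will receive the target dose of lorcaserin per weight category". In its second 6 weeks all subjects go to the maximum dose for their weight, unless tolerability prevents it.

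The one co-medication rule restated for the Extension (synopsis, Section 9.1.3, Appendix 2) is that AEDs may not be added, removed or re-dosed. A different sentence in Section 9.4.7 does run study-wide: "Investigational drugs or devices are prohibited during the participation in the study".

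**The concern.** The stated hazard comes from combining a serotonergic drug with lorcaserin, so the ban should follow lorcaserin exposure. As written it follows the phase label. A placebo subject is covered while taking placebo and loses cover on starting lorcaserin.

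The protocol itself treats the combination as dangerous. Exclusion criterion 5 requires a washout before dosing ("Use of serotonergic or other prohibited drugs administered within 7 days (or 5 half-lives, whichever is longer"; 30 days for MAO inhibitors), and Section 9.5.4.3.3 makes serotonin syndrome always reportable as serious. No benefit-risk reason is given for lifting the ban in the Extension. What is at stake is subject safety, not the efficacy inference.

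**Working it through.** The plan states no figure to reproduce. The check is a reading of scope, followed by simple counts.

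**1. Is the Extension inside the banned period?** Section 9.1 makes the Randomization Phase a 14-week Treatment Period plus a 4-week Follow-up, while Section 9.1.2 gives it 14 weeks in all. On either reading the 12-week Extension, Week 14 to Week 26, lies outside.

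**2. Could the ban be read as carrying over?** Two drafting contrasts count against that.
- The AED-stability rule in Section 9.4.7 has the same phase limit, and the protocol then wrote a separate AED rule for the Extension in three places. It did nothing similar for the banned list.
- The investigational-product sentence in the same section uses study-wide wording, so that scope was available.

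**3. Does another rule close the gap?**

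| Provision | What it does | What it leaves open |
|---|---|---|
| AED freeze (9.1.3, Appendix 2) | Bars a listed drug started as an AED | Listed drugs started for a non-seizure reason |
| Investigational-product ban (9.4.7) | Covers the whole study | Marketed drugs |
| Exclusion 5 (9.3.2) | Governs study entry | Not reapplied at Extension entry, which requires only completion of the Core Treatment Period |
| Always-serious reporting (9.5.4.3.3) | Reports an event within 24 hours | Acts after the event |
| Medication review (Table 4) | Records use at Weeks 15, 17, 20, 23 and 26 | Detects use but does not prohibit it |

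**4. Is the Extension the former placebo subjects' first exposure?** In this study, yes. Not necessarily in their lives, because exclusion 3 bars only "Use of lorcaserin within 4 weeks before Screening, or any history of it being discontinued due to lack of efficacy or adverse reactions".

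**5. Lorcaserin weeks outside the ban, for subjects who complete the Extension.**
- Former placebo: 12 / 12.
- Former lorcaserin: 12 / (14 + 12) = 12 / 26.

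These are schedule fractions and do not measure risk.

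**6. Time between scheduled medication reviews.** From Week 14 the gaps are 15 − 14 = 1, 17 − 15 = 2, 20 − 17 = 3, 23 − 20 = 3 and 26 − 23 = 3 weeks. With the ±3-day windows the longest is 21 + 3 + 3 = 27 days. A short course of a cough remedy or a triptan can start and finish inside that.

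**7. Number of subjects.** SAP Section 7 gives 22 randomized, and SAP Section 4 plans 62: 22 / 62 = 35.5%, which the SAP states as 35%. At most 22 could have entered the Extension. Assuming an exact 1:1 split, 22 / 2 = 11 were on placebo. At the SAP's assumed 12% dropout, 11 × 0.88 = 9.7, so about 10, would complete the Core Study. Neither the actual split nor the number entering the Extension is given, so former placebo entrants number between 0 and about 11 under that assumption.

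**The case against.** The strongest case against is that the gap is real on paper but matters little in practice.

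- **Section 9.5.7 is preventive.** Subjects are told to inform the site of planned care elsewhere, the investigator asks at each visit, and with consent tells the other physician about the trial. This has no phase limit and can head off a prescription. That stands as a partial safeguard, but it prohibits nothing and does not reach over-the-counter products.
- **The CYP2D6 caution in Section 9.4.7 also has no phase limit.** True, but it concerns raised exposure to other drugs, not serotonergic combination.
- **The text may be superseded.** Protocol Version 2.0 is dated 09 Jul 2020 and describes about 58 subjects at US sites. The SAP of 18 May 2024 describes about 62 subjects in several countries. A later protocol may exist and may have changed Section 9.4.7. Some pages, including what follows the visible end of Appendix 2, and the Investigator Brochure were not available. This limits the finding to the text at hand.
- **Termination leaves little to act on.** The documents do not show that anyone is still dosed, and with at most 22 subjects the listings could be compared by eye. This reduces the value of the wording change but does not make the rule correct.
- **The counts are mostly schedule arithmetic.** Fair. The rate of new starts is unknown, and minimization does not guarantee an 11/11 split.

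None of this supplies a rule that bars a new serotonergic drug during the Extension.

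**Conclusion.** The concern holds. In protocol Version 2.0, the ban justified by serotonin syndrome lapses when every subject is on lorcaserin, and following the text as written permits new starts of listed drugs for non-seizure reasons. The protocol-directed move to maximum dose also falls in this uncovered period; below 40 kg that is twice the target dose (2.5 to 5 mg BID, or 5 to 10 mg BID).

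The reach is limited. Subjects should enter the Extension already off these drugs, so only new starts matter. No harm rate can be estimated from the documents. It is worth fixing because a safety rule with a stated reason has the wrong scope and the correction is cheap. Confidence is high about what Version 2.0 says; whether any subject is still being dosed under it cannot be seen.

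**What to change.** In Section 9.4.7, the synopsis and Appendix 2, state that the banned list applies through the end of lorcaserin dosing in the Extension Phase. At minimum this should cover SSRIs, SNRIs, MAO inhibitors, triptans, bupropion, dextromethorphan, centrally acting anorectics including fenfluramine, and St. John's Wort. It would apply to any subject still or later dosed under this text.

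For subjects already treated, mark any Extension use of a listed drug in the medication listing planned in SAP Section 5.2.5, and read it beside that subject's adverse events. If nobody is still being dosed, only this marker applies.

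The cost is one sentence in three places and a flag in an existing listing, with no new tables. The downside is fewer treatment options during the Extension, for example for depression, migraine or cough.
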